## 12.2. Laboratory Evaluations

Safety laboratory samples for chemistry, hematology and urinalysis will be collected at various visits. Refer to Section 10 of the Protocol for the schedule of activities indicating when the respective samples are taken.

The following parameters will be included:

**Chemistry:** Albumin, Alanine aminotransferase, Alkaline phosphatase, Aspartate aminotransferase, Blood urea nitrogen or urea, Creatinine, Electrolytes (sodium, potassium, chloride, calcium, phosphorus), Gamma glutamyltransferase, Lactate dehydrogenase, Total bilirubin, Direct bilirubin.

**Hematology:** Full and differential blood count, Hematocrit, Hemoglobin, Mean cell hemoglobin, Mean cell hemoglobin concentration, Mean cell volume, Platelet count, Red blood cell count (% reticulocytes), White blood cell count with differential (neutrophils, lymphocytes, monocytes, eosinophils, and basophils).

**Urinalysis:** Appearance, pH, Protein, Glucose, Ketone bodies, Indicators of blood and white blood cells, Specific gravity, Urine human chorionic gonadotropin (premenopausal females only), Urobilinogen.

**Cardiovascular risk factors** (fasting condition and at Baseline and Week 16 only): C-reactive protein, Glucose, Total cholesterol, High-density lipoprotein, Low-density lipoprotein, Triglycerides. Patients should be in fasting condition (no food or fluids other than water for 8 hours) before sample collection at Baseline and Week 16.

This document is confidential.

**Serology:** HIV antibody, Hepatitis B virus, Hepatitis C virus, Hepatitis B surface antigen, Hepatitis B core antibody, Hepatitis B surface antibody, Follicle-stimulating hormone (confirmatory test for female patients in a postmenopausal status defined as cessation of menses for at least 12 months without an alternative medical cause).

**Pregnancy test:** A serum pregnancy test will be performed on all women of childbearing potential at Screening, and a urine pregnancy test will be performed at all other visits.

All summaries will be based on results in SI (standard international system of units) units and will be output in the order listed above.

Actual values and changes from baseline in chemistry and hematology will be summarized by visit using descriptive statistics.

Shift tables, showing shifts from baseline to week 16 relative to the normal ranges for chemistry and hematology will be provided. These summaries of normal range category changes illustrate the number and percentage of patients who fall into specified categories (Decrease to Low, Change to Normal or No Change, Increase to High) by comparing the baseline normal range category to the overall worst-case normal range category. The worst-case post-baseline row will be used to summarize the patients' overall worst-case normal range category change. The determination of the worst-case takes into account both planned and unscheduled assessments.

Patients with missing baseline value are to be assumed to have a normal baseline value. Worst-case can be either High or Low. If a patient has a Decrease to Low and an Increase to High during the same time interval, then the patient is counted in both the 'Decrease to Low' and 'Increase to High' categories. If a patient was high at baseline and decreases to Low during the time interval, then the patient is counted in the 'Decrease to Low' category. Likewise, if a patient was Low at baseline and increases to High during the time interval, then the patient is counted in the 'Increase to High' category. Patients are only counted in the 'Change to Normal or No Change' category if they are:

- Normal at baseline and have no normal range High and no normal range Low values during the time interval
- High at baseline and do not change to Low during the time interval
- Low at baseline and do not change to High during the time interval

All laboratory results will be included in data listings. Abnormal results for chemistry, hematology and urinalysis will be listed separately. Laboratory results for serology and pregnancy tests will be listed only.

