13. Any of the following abnormalities in clinical laboratory tests at Screening, as assessed by the study-specific laboratory and confirmed by a single repeat, if deemed necessary:
  - a. Absolute neutrophil count of  $<3.0 \times 10^9/L$  ( $<3000/\text{mm}^3$ )

This document is confidential.

- b. Hemoglobin of <10.0 g /dL or hematocrit <30%
  - c. Platelet count of <100 × 10^3 cells/mm^3 (SI: <100 × 10^9 cells/L).
  - d. Absolute lymphocyte count of <1.0 × 10^9/L (<1000/mm^3)
  - e. Total bilirubin >1.5 × the upper limit of normal (ULN); patients with a history of Gilbert's syndrome may have a direct bilirubin measured and would be eligible for this study provided the direct bilirubin is ≤ULN
  - f. Alanine aminotransferase or aspartate aminotransferase >2.5 × the ULN;
  - g. Serum creatinine ≥1.5 mg/dL. For a patient with a value of ≥1.5 mg/dL, a creatinine clearance of ≥60 mL/min (calculated using the CKD-EPI Creatinine Equation) is allowed.
14. History or evidence of hepatitis B virus (HBV) infection at Screening. Patients with positive hepatitis B surface antigen (HBsAg) are excluded. For patients with isolated positive antihepatitis B core antibody (HBcAb), hepatitis B surface antibody (HBsAb) result must also be positive to be considered for this study.
15. History or positive test result for hepatitis C virus (HCV) antibody, indicating ongoing infection, at Screening. Confirmatory testing for HCV RNA will be conducted for patients who have a positive test result. Patients who have a negative result for HCV RNA will be eligible to participate in the study.
16. History of positive HIV, or have congenital or acquired immunodeficiency (eg, common variable immunodeficiency disease). Patients who are positive for HIV antibodies (HIV-1 or HIV-2) at Screening are excluded from the study.
17. Suicidal ideation or behavior in the past 12 months as indicated by a positive response (yes) to questions 4 or 5 on the C-SSRS completed at the Screening visit or the C-SSRS completed at the Baseline visit.
18. Pregnant or breastfeeding.
19. History of alcohol or substance abuse within 6 months before Baseline that, in the opinion of the Investigator, will preclude participation in the study.
20. Institutionalized by court order or by local authority.

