14.3.4.1		Clinical Laboratory Data	
14.3.4.1.1	14.3.4.1.1	Chemistry: Summary by Visit and Change from Baseline	Safety Population
	14.3.4.1.2	Chemistry: Maximum Shift From Baseline to Week 16 Relative to the Normal Range	Safety Population
	14.3.4.1.3	Listing of Chemistry Abnormal Results	Safety Population
	14.3.4.2.1	Hematology: Summary by Visit and Change from Baseline	Safety Population
	14.3.4.2.2	Hematology: Maximum Shift From Baseline to Week 16 Relative to the Normal Range	Safety Population
	14.3.4.2.3	Listing of Hematology Abnormal Results	Safety Population
	14.3.4.3.1	Urinalysis: Summary by Visit	Safety Population
	14.3.4.3.2	Urinalysis: Maximum Shift From Baseline to Week 16 Relative to the Normal Range	Safety Population
	14.3.4.3.3	Listing of Urinalysis Abnormal Results	Safety Population
		Vital Signs	
	14.3.4.4.1	Vital Signs: Summary by Visit and Change from Baseline	Safety Population
		ECG	

This document is confidential.

Header	Table Number	Name	Analysis Population
	14.3.4.4.2.1	ECG Parameters: Summary by Visit and Change from Baseline	Safety Population
	14.3.4.4.2.2	ECG Outlier Analysis by Visit	Safety Population
	14.3.4.4.2.3	ECG Outlier Analysis at Any Time Post-baseline	Safety Population
		Physical Examination	
	14.3.4.4.3	Shift in Physical Examination between Baseline and each Visit	Safety Population
		Other Safety	
	14.3.4.4.4.1	Hospital Anxiety and Depression Scale (HADS): Summary by Visit and Change from Baseline	Safety Population
	14.3.4.4.4.2	Hospital Anxiety and Depression Scale (HADS): Summary by Category and Visit	Safety Population
	14.3.4.4.4.3	Hospital Anxiety and Depression Scale (HADS): Shift from Baseline	Safety Population
	14.3.4.4.5	Number of Patients with Suicidal Ideation, Suicidal Behavior, and Self-injurious Behavior without Suicidal Intent Based on the C-SSRS	Safety Population
	14.3.4.4.6	Shift in C-SSRS between Baseline and each Visit	Safety Population

This document is confidential.

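### The laboratory shift tables cannot show worsening in a patient already out of range at Baseline, and count it together with normalisation

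*SAP*

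**What the plan says.** SAP section 12.2 builds the chemistry and hematology shift tables "by comparing the baseline normal range category to the overall worst-case normal range category". There are three result categories: *Decrease to Low*, *Change to Normal or No Change* (below, the middle category) and *Increase to High*. The worst case draws on planned and unscheduled values.

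The middle category is closed by a list: "Patients are only counted in the 'Change to Normal or No Change' category if they are" one of three things. The first is Normal at Baseline with no High or Low value afterwards. The second is "High at baseline and do not change to Low during the time interval". The third is "Low at baseline and do not change to High during the time interval". A separate sentence covers crossing the whole range: "If a patient was high at baseline and decreases to Low during the time interval", the patient goes to *Decrease to Low*, and the reverse holds for Low to High. On missing Baselines: "Patients with missing baseline value are to be assumed to have a normal baseline value".

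The table index (SAP section 18) carries this through as Table 14.3.4.1.2, "Chemistry: Maximum Shift From Baseline to Week 16 Relative to the Normal Range", and Table 14.3.4.2.2 for hematology.

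On who may enter, exclusion criterion 13 applies at Screening. For transaminases it excludes only "Alanine aminotransferase or aspartate aminotransferase >2.5 × the ULN". For total bilirubin the limit is 1.5 times ULN, with an allowance for Gilbert's syndrome.

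**The concern.** A shift table is read as a count of patients whose results got worse. Here the middle category merges three different courses: returning to normal, staying put, and moving further out of range on the same side. Its label mentions only the first two. The entry limits make the third course possible for liver tests from the first dose.

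Safety is part of the primary objective, and the secondary objective is to find the dose with the best benefit/risk ratio. SAP section 12 plans no inferential safety analysis, so the comparison of arms rests on descriptive tables. The normal-range shift tables are the only categorical laboratory tables. If worsening from an abnormal Baseline differed by dose, they could not show it.

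**Working it through.** The point concerns a classification rule, so the plan states no figure to reproduce. The check applies the rule to every possible case and then looks at what the other outputs add.

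**Step 1: the rule.** Let B be the Baseline category (missing set to Normal) and P the set of categories reached after Baseline.

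- *Decrease to Low* if B is not Low and P contains Low.
- *Increase to High* if B is not High and P contains High.
- Middle category if B is Normal and P contains neither Low nor High, or B is High and P lacks Low, or B is Low and P lacks High.

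**Step 2: all cases.** Four Baseline states (Low, Normal, High, missing) times seven non-empty sets P give 4 × 7 = 28 combinations.

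| Baseline | Reached after Baseline | Counted as |
|---|---|---|
| High | {Normal}, {High}, {Normal, High} | Middle category |
| High | the four sets containing Low | Decrease to Low |
| Low | {Normal}, {Low}, {Low, Normal} | Middle category |
| Low | the four sets containing High | Increase to High |
| Normal or missing | {Normal} | Middle category |
| Normal or missing | {High}, {Normal, High} | Increase to High |
| Normal or missing | {Low}, {Low, Normal} | Decrease to Low |
| Normal or missing | {Low, High}, {Low, Normal, High} | Both |

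The count is 3 + 4 + 3 + 4 + 2 × (1 + 2 + 2 + 2) = 28. No combination starting from High leads to *Increase to High*, and none starting from Low leads to *Decrease to Low*.

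**Step 3: illustrative ALT values**, in multiples of ULN. These are chosen to exercise the rule and are not data from the documents.

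| Baseline | Worst after Baseline | Counted as |
|---|---|---|
| 2.4 | 0.9 | Middle category |
| 1.5 | 1.5 | Middle category |
| 1.1 | 3.5 | Middle category |
| 2.4 | 5.5 | Middle category |
| 2.4 | 21 | Middle category |
| 0.9 | 1.1 | Increase to High |
| 0.9 | 20 | Increase to High |

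The first five rows share one cell. The last two share another, so a rise from Normal is counted, but its size is lost.

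**Step 4: can such patients enter?** Yes. ALT or AST above 1 and up to 2.5 times ULN is High and is not excluded. The same holds for bilirubin above 1 and up to 1.5 times ULN. The limits apply at Screening, while SAP section 7.2 takes Baseline as the last value before first dose, so the Baseline value may differ. On the Low side, criterion 13 sets floors for neutrophils, lymphocytes, platelets and hemoglobin. Whether values above those floors can still be Low depends on the laboratory's ranges, which the documents do not give.

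**Step 5: what the other outputs add.**

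- *By-visit summaries* (SAP sections 7.1 and 12.2) give values and changes with mean, SD, median, quartiles, minimum and maximum per arm. An extreme at a scheduled visit shows as a maximum, but not as a count of patients and not against that patient's Baseline. Unscheduled values are generally left out unless they fill a missing visit (SAP sections 7.1 and 7.4). The protocol schedules post-Baseline safety laboratory tests only at Weeks 4, 8 and 16 and asks for repeat testing of clinically significant values. A peak at an unscheduled repeat would therefore normally reach only the shift table among the laboratory summaries.
- *Listings* of abnormal chemistry and hematology results (14.3.4.1.3 and 14.3.4.2.3) show the values patient by patient, without counts.
- *Adverse events*: results the investigator judges clinically significant are to be treated as adverse events (protocol section 12.6). A condition present at Screening that deteriorates is to be recorded as one (protocol section 12.9.1). These are graded by CTCAE v5 and tabulated by maximum grade, but only once reported.
- *ECG, by contrast*: SAP section 12.4 counts patients by QTc threshold and by increase from Baseline, at each visit and at any time. The index holds no laboratory equivalent.

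**The case against.** The strongest reply is that the table does what its title says. It reports changes of normal-range category, and High to High is no change of category. The data are not lost: the by-visit maximum would expose an extreme scheduled value, Section 14 lists the abnormal results, and with about 50 patients per arm a very high ALT is unlikely to escape the listing or the investigator. No AESI is defined by a laboratory value, and protocol section 5.4.1 reports no clinically relevant laboratory findings for the modified-release tablet in healthy volunteers. A ULN table could also be produced afterwards.

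Much of this stands, and it limits the point. It does not answer the merging of stability and further worsening with normalisation, or the absence of any laboratory count by magnitude. A table added after unblinding is also weaker than one planned in advance.

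Stronger readings are tempting but unsupported:

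- *That the worst laboratory worsening in general is labelled as no change.* Only patients already out of range on the same side are affected. A rise from Normal to 20 times ULN is counted as *Increase to High*.
- *That every High patient falls in the middle category.* One who also goes Low is counted in *Decrease to Low*.
- *That the affected patients are those most likely to worsen, or are a known share of each arm.* The documents give no basis for either statement.

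**Conclusion.** The point holds in limited form. The shift tables in SAP section 12.2 cannot show worsening within an already abnormal category, and they count it with normalisation. Of the seven post-Baseline patterns open to a patient High at Baseline, three go to the middle category and four to *Decrease to Low*; Low at Baseline is the mirror image. Rises from Normal are counted without magnitude.

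The conclusion follows from the stated rule and needs no assumption about prevalence. The number of patients affected cannot be given, because the documents do not report how many start outside the range. No hypothesis test, sample size, alpha level or data collection is touched. The change is worth making because a planned safety count can mislead, the trial admits patients to whom it applies, and the SAP already uses a count by magnitude for QTc.

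**What to change.** In SAP section 12.2 and Tables 14.3.4.1.2 and 14.3.4.2.2:

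1. Separate *Change to Normal* from *No Change*.
2. Add a by-arm table of Baseline against worst post-Baseline CTCAE v5 grade for each gradable test, using planned and unscheduled values. This grading is already in use for adverse events.
3. If the full grade table is not wanted, give as a minimum the by-arm counts of maximum post-Baseline ALT, AST and bilirubin by multiple of ULN and by Baseline category, with cut-points fixed before unblinding.

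A grade table still merges worsening within a single grade, but in finer steps than Low, Normal and High.

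The cost is SAP wording and programming on data already collected, and one or two larger descriptive tables. Nothing changes in trial conduct.

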### 12.3. Vital Signs

Heart rate (beats per minute [bpm]), respiratory rate (breaths per minute), systolic and diastolic blood pressure (mmHg) and body temperature (degree Celsius) will be measured at different visits as per the SoA in Protocol Section 10.

The conversion for temperature is as follows: Temperature (in °C) = 5/9 (Temperature [in °F]-32).

Actual values and changes from baseline in vital sign measurements will be summarized by visit using descriptive statistics.

This document is confidential.

All vital signs will be provided in data listings.

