5.3. Clinical Risks/Benefits

Despite the positive and encouraging efficacy results of the Phase 2a study of the immediate-release tablets of orismilast, this formulation presented an undesirable safety profile with 50% of patients prematurely discontinuing because of GI effects. To improve the GI tolerance, several formulations were tested in an extensive Phase 1 clinical program, leading to the selection of a modified-release formulation with notably better GI tolerance in healthy volunteers. The modified-release formula is expected to mitigate potential GI effects previously observed in psoriasis patients with the immediate-release tablets while maintaining the efficacy previously observed. The titration dosing schedule at the initiation of study treatment will help to reduce the incidence and severity of GI side effects that tend to occur primarily when starting therapy. The improved safety profile of the modified-release formulation is expected to make the therapeutic window of orismilast wider this allowing to achieve dosing levels with adequate efficacy and good tolerability.

Occurrence and severity of GI disorders will be promptly identified by monitoring the subjects for any signs of abdominal discomfort, abdominal distension, abdominal pain, nausea, vomiting, loss of appetite, and diarrhea. Depending on their severity, these AEs may qualify as an adverse event of special interest (AESI). Based on the occurrence of GI or other AEs considered having a causal relationship with study treatment, the Investigator might consider decreasing the daily dosing regimen or stopping the treatment for a few days, until recovery. Besides the above, all subjects will be monitored for any cardiovascular manifestations using vital signs and 12-lead ECG at each visit. Drug class potential effects such as weight loss and major depression will be monitored during the study. Subjects with major depression, presenting major psychiatric disorders or at risk for suicide will be excluded from enrollment, and suicidal ideation and depressive symptoms will be assessed in the course of the study by Columbia-Suicide Severity Rating Scale (C-SSRS) and Hospital Anxiety and Depression Scale (HADS), respectively. Patients will be informed of the potential increased risk of depression or suicidal thoughts of this class of drugs; and recommended to promptly contact their study doctor in case of such event.

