12.2. Vital Signs

Vital signs (body temperature, respiration rate, heart rate, and systolic and diastolic blood pressure measurements) will be evaluated at the visits indicated in the Schedule of Assessments (Table 4). Using of tympanic/ear thermometer is recommended for body temperature.

All vital signs will be measured after the patient has been resting in a sitting position for at least 5 minutes. Blood pressure measurements are to be taken in the same arm for the duration of the study. Body weight (without shoes) will be recorded whenever vital signs are recorded; height (without shoes) will be recorded at Baseline only. A weight reduction of at least 5% from Baseline should be reported as a TEAE.

Vital sign measurements will be repeated if clinically significant or machine/equipment errors occur. Out-of-range blood pressure, respiratory rate, or heart rate measurements will be repeated at the Investigator's discretion. Any confirmed, clinically significant vital sign measurements must be recorded as AEs on the eCRF.

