12.9.2. Adverse Events of Special Interest

An AESI (serious or non-serious) is one of scientific and medical concern, for which ongoing monitoring and rapid communication by the Investigator to the sponsor could be appropriate. AESIs must be reported within 24 hours of occurrence or when the Investigator becomes aware of the event, following SAE reporting procedures (Section 12.9.4). Such an event might require

further investigation in order to characterize and understand it. Depending on the nature of the event, rapid communication by the trial sponsor to other parties (eg, regulators) might also be warranted.

In this trial, the following AEs are to be considered AESIs:

- Any AE of occurrence of suicidal ideation or behavior, including a positive response to question 1 to 5 of C-SSRS
- A depression assessed as moderate or worse by the Investigator or a score ≥15 in the HADS score
- Any grade 3 or higher psychiatric condition
- Any weight loss >5% compared to Baseline, and/or
- Any of the following GI TEAEs: vomiting, diarrhea with an increase of at least four stools per day over Baseline (Grade 2 CTCAE) for at least 3 days.

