15.4. Safety Analysis

All safety analyses will be conducted using the Safety Analysis Population. AE data will be presented and tabulated according to Medical Dictionary for Regulatory Activities (MedDRA) classification. Reported AEs will be summarized by the number of patients reporting the events, as well as by SOC and Preferred Term (PT), SOC, PT, and severity, and SOC, PT, and relationship to study drug.

Laboratory (chemistry and hematology) parameters and vital signs will be tabulated by visit using descriptive statistics and shift tables. The value at each visit, as well as the change from Baseline, will be presented.

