### 5.5. Safety Endpoints

- The occurrence, severity, and seriousness of treatment-emergent adverse events (TEAEs) reported over the 16-week Treatment Period and the 4-week Follow-up Period.

This document is confidential.

- Changes from Baseline in physical examination; vital sign measurements (body temperature, respiration rate, heart rate, and systolic and diastolic blood pressure measurements); and body weight over the 16-week Treatment Period and the 4-week Follow-up Period.
- Changes from Baseline in electrocardiogram (ECG) findings over the 16-week Treatment Period and the 4-week Follow-up Period.
- Changes from Baseline in safety laboratory values (hematology, serum chemistry, and urinalysis) over the 16-week Treatment Period and the 4-week Follow-up Period.
- HADS at each visit except Week 2.
- C-SSRS at each visit except Weeks 1 and 2.

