14.2.3		Exploratory Parameters	
	14.2.3.1	Change from Baseline in Physician's Global Assessment of Finger Nails (PGA-F) at Week 16 Exploratory Analysis: Descriptive Statistics	ITT Population
	14.2.3.2	Change in Scalp-Specific Investigator Global Assessment (ss-IGA) from Baseline at Week 16 Exploratory Analysis: Descriptive Statistics	ITT Population - Patients with Baseline Score of at least 2 (Mild Scalp Psoriasis)
	14.2.3.3	Change from Baseline of Scalp Itch Numeric Rating Scale (NRS) at Week 16 Exploratory Analysis: Descriptive Statistics	ITT Population - Patients with Baseline Score of at least 4 on the 11-point NRS
	14.2.3.4	[REDACTED] [REDACTED] Exploratory Analysis: Descriptive Statistics	ITT Population - [REDACTED] [REDACTED] [REDACTED] [REDACTED] [REDACTED]
	14.2.3.5	Change in Cardiovascular Risk Factors at Week 16 Exploratory Analysis: Descriptive Statistics	ITT Population

This document is confidential.

Header	Table Number	Name	Analysis Population
	14.2.3.6.1	Trough Levels of Orismilast and Metabolites Exploratory Analysis: Descriptive Statistics	ITT Population
	14.2.3.6.2	Plasma Levels of Orismilast and Metabolites Exploratory Analysis: Descriptive Statistics	ITT Population - Patients Having Accepted The Additional Profiles
	14.2.3.6.3	Trough Levels of Orismilast and Metabolites by Time Since Previous Dose Exploratory Analysis: Descriptive Statistics	ITT Population
	14.2.3.7	[REDACTED] [REDACTED] Exploratory Analysis: Descriptive Statistics	ITT Population
14.3		Safety Data	
14.3.1		Displays of Adverse Events	
	14.3.1.1	Overall Summary of Treatment Emergent Adverse Events (TEAEs)	Safety Population
	14.3.1.2	Treatment Emergent Adverse Events (TEAEs) by System Organ Class and Preferred Term Safety Population	Safety Population
	14.3.1.3	Treatment Emergent Adverse Events (TEAEs) by System Organ Class, Preferred Term and Maximum Toxicity Grade	Safety Population
	14.3.1.4	Treatment Emergent Adverse Events (TEAEs) by System Organ Class, Preferred Term and Toxicity Grade	Safety Population
	14.3.1.5	Treatment Emergent Adverse Events (TEAEs) by System Organ Class, Preferred Term and Maximum Relationship	Safety Population
	14.3.1.6	Treatment Emergent Adverse Events (TEAEs) by System Organ Class, Preferred Term and Relationship	Safety Population
	14.3.1.7	Treatment Emergent Serious Adverse Events (TESAEs) by System Organ Class and Preferred Term	Safety Population

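### The SAP plans no by-visit summary of measured body weight, although weight change over treatment and follow-up is a safety endpoint and weight loss a named class effect

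*SAP*

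**What the plan says.** **Endpoint.** SAP 5.5, like Protocol 6.2.2.3, names changes from Baseline in vital signs "and body weight over the 16-week Treatment Period and the 4-week Follow-up Period" as a safety endpoint.

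**Risk.** Protocol 5.3: "Drug class potential effects such as weight loss and major depression will be monitored during the study". Protocol 12.9.2 includes among the AEs of special interest "Any weight loss >5% compared to Baseline, and/or". Protocol 12.2 asks for a loss of at least 5% to be reported as a TEAE.

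**Measurement.** Protocol 12.2: "Body weight (without shoes) will be recorded whenever vital signs are recorded". The Schedule of Assessments (Protocol Table 4) marks weight at Screening, Day 1 and Weeks 4, 8, 12, 16 and 20.

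**Analysis.** SAP 12.3 gives the vital signs as "Heart rate (beats per minute [bpm]), respiratory rate (breaths per minute), systolic and diastolic blood pressure (mmHg) and body temperature (degree Celsius", summarised descriptively by visit. The index (SAP 18) has one vital-sign table, 14.3.4.4.1, and no weight table. Weight belongs to the cardiovascular panel of SAP 9.2.3, which leads to Table 14.2.3.5, "Change in Cardiovascular Risk Factors at Week 16 Exploratory Analysis: Descriptive Statistics". The matching listing, 16.2.6.3.5, covers Baseline and Week 16.

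**Shift tables.** Protocol 15.4 says that laboratory "parameters and vital signs will be tabulated by visit using descriptive statistics and shift tables". SAP 12.3 and the index contain no vital-sign shift table.

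**The concern.** The endpoint covers the whole 20 weeks, but the planned summary of measured weight covers one visit. The trial's secondary objective is to choose the dose with the best balance of benefit and risk, and weight loss is one of the two class effects that Protocol 5.3 names. Without weight by visit, the clinical study report could not show how much weight each dose group lost, how early, or whether it returned after treatment.

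The single tabulated visit is also one that patients who stop early may not reach. If gastrointestinal intolerance leads both to weight loss and to stopping, the patients of most interest contribute measured weights at Weeks 4 to 12 that enter no table. Site-reported events cover part of this, but only when the site works out the percentage and enters the event.

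**Working it through.** The plan states no figure on this point, so the check sets the passages side by side. The arithmetic only gives scale.

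**1. Visits measured against visits tabulated.**

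| Visit | Weight measured (Protocol Table 4) | Planned summary of measured weight |
|---|---|---|
| Baseline | yes | demographics table (SAP 8.3) |
| Week 4 | yes | none |
| Week 8 | yes | none |
| Week 12 | yes | none |
| Week 16 | yes | Table 14.2.3.5, exploratory |
| Week 20 | yes | none |

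Tabulated post-baseline visits: 1 of 5, or 20%.

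**2. Comparison with other safety measures in the same SAP.** Depression, named beside weight loss in Protocol 5.3, is covered by the HADS by-visit summary, a category table and a shift table (SAP 12.6). QTc has threshold counts at each visit and at any time (SAP 12.4). Measured weight has neither, although the protocol gives it a threshold.

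**3. Who can appear in the Week 16 table.** Under SAP 7.4, the EoT record of a patient who discontinued treatment counts as Week 16 only if taken on Day 99 to 139, that is 99 − 112 = −13 to 139 − 112 = +27 days from target. An earlier EoT record goes to Week 4, 8 or 12, or stays as EoT. That patient's later visit is labelled Follow-up. Protocol 8.4 asks for EoT assessments within 4 weeks (28 days) of the last dose. If that is followed, an EoT record can reach Day 99 only when the last dose was on or after Day 99 − 28 = 71. A patient whose last dose came before Day 71 would need some other weight, such as an unscheduled one, to be counted at Week 16. SAP 7.3 leaves missing data as missing except where stated, and no imputation is stated for exploratory endpoints.

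**4. Scale.** No discontinuation rate is given for this formulation. As an assumption, let 10% to 50% of an arm of 50 stop too early to have a Week 16 weight:

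- 10%: 50 × 0.10 = 5 absent, 45 remain.
- 50%: 50 × 0.50 = 25 absent, 25 remain.

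The upper end is the share of orismilast patients with AEs leading to withdrawal in the Phase 2a trial (Protocol 5.2.2.3), which used immediate-release tablets.

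**5. What the adverse-event tables capture.** Reported losses enter the TEAE table (14.3.1.2) and, as AESIs, Table 14.3.1.17 and Listing 14.3.2.2. Treatment-emergent means up to 7 days after the last dose (SAP 12.1). Week 20 is nominally 28 days after Week 16, and 28 > 7, so a loss that starts well after treatment ends falls outside those tables. If reported, it appears in Table 14.3.1.18 (AEs starting in follow-up). A loss that no site reports is in no planned count. None of these tables gives a mean change, a distribution or a course over time.

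**6. Threshold.** Protocol 12.2 uses at least 5% (TEAE) and Protocol 12.9.2 uses above 5% (AESI). A loss of exactly 5% meets one and not the other.

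**7. Shift tables.** Protocol 12.2 defines vital signs by the same parameters as SAP 12.3, and Protocol 6.2.2.3 names body weight alongside them, as a separate item. The missing shift tables are therefore a different matter from the missing weight summary. The legible text of SAP 14 declares only the added randomized population.

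**The case against.** **The adverse-event route already exists.** This is the strongest reply, and it largely stands for detecting events. Losses of about 5% are to be reported, and the TEAE and AESI tables show them by arm in the Safety Population, including for patients who later stop. A reader might infer that a loss first seen at Week 20 would be counted nowhere; Table 14.3.1.18 rules that out for reported events. What the route lacks is size, time course and a check on site reporting.

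**The endpoint is reported.** A reader might infer that the SAP leaves the endpoint out altogether. It does not: Week 16 weight is in Table 14.2.3.5. The reporting is incomplete, not absent.

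**Bias is not shown.** A reader might infer that a Week 16 mean favours drug. The documents contain no weight data for patients who stopped. In Phase 2a about half of both groups withdrew, for different reasons (Protocol 5.2.2.2), and the present formulation was chosen for better tolerability. Late stoppers can still fall in the Week 16 window, unscheduled weights may fill gaps, and patients off drug remain in the study for safety evaluation (Protocol 8.4, 9.3), although their visit schedule is not set out. Selective absence is plausible; its direction and size are unknown.

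**The population label is harmless.** ITT and Safety contain the same patients under SAP 6.2 and 6.3 and differ only in whether the arm is as randomised or as received.

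**Other outputs might include weight.** The table shells are a separate document (SAP 21), and SAP 7.1 says generally that all data are listed. Neither obliges anyone to summarise weight by visit.

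**The SAP prevails over the protocol.** Protocol Section 15 says so, and this covers the shift tables. It does not remove the need to declare the change in SAP 14.

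**Conclusion.** The point holds as a gap in reporting. As written, the plan summarises measured weight at 1 of 5 post-baseline visits, in an exploratory table, for a safety endpoint that spans treatment and follow-up and concerns a named class effect. Patients without a record assigned to Week 16 are absent from that table. Under the assumed 10% to 50%, that is 5 to 25 of 50 per arm. This range is illustrative: it equates stopping early with having no Week 16 weight, and its upper end comes from another formulation.

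The documents do not support saying that weight loss would go unseen, that the Week 16 result is known to favour drug, or that dropping the shift tables caused the gap. The shift tables are a separate, undeclared departure from Protocol 15.4 and would not have covered weight. The efficacy analyses are unaffected. What suffers is the comparison of benefit and risk across doses. The conclusion rests on the public text of the SAP and its index; the shells could not be seen.

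**What to change.** 1. In SAP 12.3 and Table 14.3.4.4.1, add body weight (actual value, change and percentage change from Baseline) at Weeks 4, 8, 12, 16, EoT and 20/Follow-up, in the Safety Population.
2. Reconcile the weight-loss wording of Protocol 12.2 (at least 5%) with that of Protocol 12.9.2 (above 5%). Then add one table per arm counting patients whose measured loss reaches the threshold at each visit and at any post-baseline time, including unscheduled and follow-up weights. The QTc outlier tables of SAP 12.4 can serve as the model.
3. Separately, restore the vital-sign shift tables of Protocol 15.4, with their categories defined because neither document gives any, or declare their removal in SAP 14.

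Items 1 and 3 need SAP wording and a few outputs from data already collected, with no new assessment. Item 2 needs one more table and a clarification of the threshold used for the count.
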